The non-vitamin K oral anticoagulants (NOACs) are a new group of drugs which have been recently approved for use as blood thinners. They have a faster onset of action compared to warfarin and unlike warfarin, they do not need frequent monitoring. Apixaban and Rivaroxaban both have a similar mechanism of action. They inhibit Factor 10 which a clotting factor. They are the most commonly prescribed NOACs at Einstein Medical Center Philadelphia. We intend to serially monitor the kidney function by measuring the serum creatinine and urinalysis of 40 high risk patients who are recently started on either apixaban or rivaroxaban over a six month period. This will enable us to discover what proportion of patients actually develop ARN after starting a NOAC.

2) Project Objectives and Hypotheses:

Determine the incidence of ARN in high risk patients on rivaroxaban or apixaban (Factor 10 inhibitors).

Hypothesis - the incidence of ARN with apixaban or rivaroxaban is less than the previously reported incidence of ARN in warfarin.

- Describe demographic and urinalysis-associated predictors of ARN in patients on rivaroxaban or apixaban (Factor 10 inhibitors)

3) Background/Significance of Research (*Provide the scientific or scholarly background and rationale for the research based on the existing literature (include references). Describe relevant prior experience and gaps in current knowledge. Describe any relevant preliminary data. Explain the significance of the research in terms of why it's important and how it will add to existing knowledge.*):

Anticoagulation-related nephropathy (ARN) is an understudied renal complication of anticoagulant therapy that is characterized by acute kidney injury (AKI) defined as an increase in baseline serum creatinine ≥ 0.3 mg/dL, without any alternate etiology, in the setting of a supra-therapeutic International Normalized Ratio (INR) greater than 3.0 [1-7]. ARN has mainly been studied in relation to warfarin, it usually occurs in the first two months of starting anticoagulant therapy and retrospective studies have estimated the prevalence to range from 16% to 37% [4-6]. The strongest risk factor for ARN is pre-existing chronic kidney disease (CKD); other risk factors include older age, diabetes mellitus and hypertension [1,4]. Patients with ARN have an accelerated progression of CKD and a retrospective study of more than 15,000 patients on warfarin showed a 65% increase in mortality in patients with ARN [4,6].

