- Montgomery campus
- Other: please specify -

b. Indicate if human research will be conducted at external location(s) overseen by the AEHN investigator (e.g. private physician office, collaborating hospital/university)

- Yes (Complete Appendix B: External Site Approvals on Application for Human Research)
- No

5) Resources available to conduct the Human Research:

a. Target population (e.g. Adult subjects with a diagnosis of Type II diabetes for greater than two years?": Elderly patients with CKD who have recently been started on Rivaroxaban or Apixaban

b. For prospective studies:

- i.) Total number of subjects planned to be enrolled in the study at AEHN site(s): 40
- ii) For multi-site projects, please indicate total number of subjects planned to be enrolled in the study at all sites: 0
- iii) Describe access to a population that would allow recruitment of the targeted number of subjects (*i.e. how many potential subjects do you have access to? What percentage of those potential subjects do you need to recruit?*) : We estimate that around 100 patients meeting our criteria are started on Apixaban or Rivaroxaban in a six-month period. We anticipate to recruit 40% (40) of them into the study

c. For retrospective studies:

- i.) Estimated number of charts to be reviewed: N/A
- ii.) Time period of interest for data being collected (*e.g. Subjects who had XX procedure between 6/1/00 and 6/1/05*): N/A

d. Describe the number and qualifications of the study team members, their experience in conducting research, their knowledge of the local study site(s), culture, and society:

Principal Investigator: [name] is a first year intern in Internal Medicine at Albert Einstein Medical Center. [name] completed her medical school training at the University of Jordan in Jordan where she graduated top of her class. She completed a graduate degree in Public Health at Thomas Jefferson University in Philadelphia and she is interested in population epidemiology and determinants of health. At Einstein, he has been very keen to work on research projects with collaboration with other colleagues on various projects

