Screening will be also be carried out by a query on the electronic medical record with a confidential report generated weekly by the Einstein's AECIS which will contain all rivaroxaban and apixaban prescriptions ordered by electronic scripts. Investigators and co-investigators will review the medical records of patients on the list to determine if they meet the inclusion criteria for the study.

Identified patients will be given a written description about the study and [name] (principal investigator) will be notified. All identified patients will have their medical records/chart reviewed by [name] to determine eligibility for the study. If appropriate, he will then contact them by phone and arrange a meeting to discuss the study protocol, answer any questions and complete the consent process

- ii. Describe the criteria that define who will be included or excluded in your final study sample:

Inclusion Criteria

- Age \geq 60 years
- GFR \leq 90 ml/L based on creatinine clearance
- Participant has been initiated on long term anticoagulation with rivaroxaban or apixaban for atrial fibrillation within four weeks of recruitment
- Participant is willing to comply with all aspects of the protocol, including adherence to medical therapy and follow-up visit
- Participant is willing to give written informed consent

Exclusion Criteria

- History of blood dyscrasias or active bleeding,
- History of hematuria
- Patients on dialysis

c. Study Timelines:

- i. Duration of an individual subject's participation in the study: 6 months
- ii. Time period anticipated to enroll all study subjects or to complete chart review: 4 months
- iii. Estimated overall study duration (*i.e. from initiation to completion of primary analyses*): 12 months

d. Study Endpoints:

- i. Describe the primary and secondary study endpoints (*i.e. the outcome(s) that the study is designed to evaluate*):

Primary endpoint - Incidence of ARN is the primary outcome of this study and this is based on a documentation of AKI (defined as an increase in baseline serum creatinine \geq 0.3 mg/dL), in the absence of any other obvious etiology for the AKI identified after a standard clinical evaluation and work up by the patient's primary care physician, cardiologist or nephrologist. This incidence will be expressed as a percentage.

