- i. Describe steps that will be taken to secure the data (e.g. training, authorization of access, password protection, encryption, physical controls, certificates of confidentiality and separation of identifiers and data) during storage, use and transmission: As stated above, a study participant list containing identifiable data will be password protected and stored on the Einstein system. This list will only be able to be accessed by members of the research team. All other data will be stored in a separate database with unique but unidentifiable identification numbers. At the termination of the study the initial study participant list will be deleted.
- ii. Describe the data analysis plan, including any statistical procedures and method for determining the sample size for the study:

Incidence of ARN is the primary outcome of this study and this is based on a documentation of AKI (defined as an increase in baseline serum creatinine ≥ 0.3 mg/dL), in the absence of any other obvious etiology for the AKI identified after a standard clinical evaluation and work up by the patient's primary care physician, cardiologist or nephrologist. This incidence will be expressed as a percentage.

Urinalysis measurements (particularly hematuria and proteinuria) will be analyzed for correlation with the incidence of ARN. Demographic variables including age and race will be analyzed in contingency tables using Fisher's exact test to ascertain if they are significant for the primary outcome.

There is no data at all in the literature for the incidence of ARN with rivaroxaban or apixaban and we short-listed that number (40) based on the reported incidence for warfarin (17-37%). We are selecting the patients at highest risk (elderly, CKD) for anticoagulation-related nephropathy (ARN) and we expect that the incidence we obtain will be the highest for the population we are studying.

In terms of precision, we will calculate confidence intervals of the proportional incidence using Stata (command line `cii 40 (incidence)`). If the incidence is zero, Stata calculates the 95% confidence interval based on our sample size as 0-9%. If we only find 2 cases of ARN, Stata calculates the point estimate incidence at 5% with 95% confidence interval as 0.6% - 17%, If we find 10 cases of ARN, Stata calculates the point estimate incidence as 25% with 95%

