confidence interval as 13% to 41%, etc. Our sample is elderly, CKD subjects at higher risk hence we expect a higher incidence than in the normal population, hence a negative result will suggest very low risk in the general population.

- iii. Describe where and how data will be stored locally: Data will be stored in password protected spreadsheets on the Einstein computer network.
- iv. Specify how long data will be stored locally: 6 years after publication of the study
- v. Specify who will have access to the data locally: The research team members.
- vi. Describe process that will be followed to ensure accuracy of collected data: All data will be checked twice upon entering it into the database to ensure accuracy. All calculations and statistical tests will be confirmed by both members of the team.
- vii. Will data be sent out or received: No Yes
 - a. Who is responsible for receipt or transmission of the data? N/A
 - b. How will the data be transported? N/A

h. Provisions to monitor the data for the safety of subjects (Required only when Human Research involves more than minimal risk):

- i. Describe plans to periodically evaluate the data collected regarding both harms and benefits to determine whether subjects remain safe. Include what data will be reviewed, who will review the data and when the data will be reviewed:

This research has no additional risk above and beyond that of a blood draw and urine collection. Blood draws for serum creatinine assay will be performed by a trained phlebotomist using standard techniques. Any problems encountered during blood draws will be reported to the research staff and will be reviewed by the entire research study team as soon as they occur to determine if and when the event needs to be reported to the IRB, and if the protocol and/or consent document require modification. Each safety data will be reviewed by at least 2 members of the research team and all events will be reviewed after every 10 patients are recruited.

i. Withdrawal of Subjects:

- i. Describe the anticipated circumstances under which subjects will be withdrawn from the research without their consent: Subjects will be censored from the study if anticoagulation is withdrawn for any clinical reason

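### The renal entry rule does not ensure the elderly CKD, highest-risk cohort on which the protocol rests its expected incidence and its reading of a negative result

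*Protocol*

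**What the plan says.** Three places in the protocol describe who is studied:

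- Section 5(a), target population: "Elderly patients with CKD who have recently been started on Rivaroxaban or Apixaban".
- Data analysis plan (Study Design, item g.ii), explaining the sample size: "We are selecting the patients at highest risk (elderly, CKD) for anticoagulation-related nephropathy (ARN"). The same sentence expects the incidence obtained to be the highest for this population.
- The end of that item: "Our sample is elderly, CKD subjects at higher risk hence we expect a higher incidence than in the normal population". From this it concludes that a negative result points to a very low risk in people generally.

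The criteria that decide who enters are in Study Design, item b.ii. They require age 60 or over, GFR at or below "90 ml/L based on creatinine clearance", rivaroxaban or apixaban begun for atrial fibrillation within the four weeks before recruitment, willingness to comply, and consent. The exclusions are blood dyscrasia or active bleeding, past hematuria, and "Patients on dialysis". Nothing asks for a CKD diagnosis, a duration of impairment, proteinuria or another sign of kidney damage.

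Section 3 names CKD as the strongest risk factor for ARN. Section 2 hypothesises an incidence below that reported for warfarin.

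**The concern.** The argument in the analysis plan is a worst-case argument: study the patients most likely to develop ARN, and if few do, others should be safer still. It works only as far as the entry rule actually selects those patients. Creatinine clearance falls with age, so at 60 and over a ceiling of 90 can be met by someone whose creatinine is ordinary and who has no kidney disease.

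If such patients make up a sizeable part of the cohort, the single reported percentage is not an incidence in CKD patients. A low figure could then come partly from the case mix rather than from the drugs. That error runs in one direction, toward the hypothesis that ARN is less frequent than with warfarin.

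**Working it through.** **Step 1. The protocol's own intervals.** Inputs from the protocol: n = 40 (section 5(b)), 95% confidence, and 0, 2 or 10 cases (analysis plan). With the exact binomial (Clopper-Pearson) method:

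| Cases / n | Recomputed | Stated |
|---|---|---|
| 0/40 | 0 to 8.8% | 0-9% |
| 2/40 | 0.6% to 16.9% | 0.6%-17% |
| 10/40 | 12.7% to 41.2% | 13%-41% |

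For zero cases the upper limit is 1 − 0.025^(1/n), here 1 − 0.025^(1/40) = 8.8%. All three intervals reproduce, so the arithmetic is not at issue.

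**Step 2. Whom the clearance ceiling admits.** The protocol names no formula. Assume Cockcroft-Gault: clearance = (140 − age) × weight / (72 × creatinine), multiplied by 0.85 for women. Weights and creatinine values are illustrations, not protocol data.

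- Man, 60 y, 80 kg, 1.0 mg/dL: 80 × 80 / 72 = 89. Admitted.
- Man, 70 y, 80 kg, 1.0 mg/dL: 70 × 80 / 72 = 78. Admitted.
- Woman, 70 y, 70 kg, 0.8 mg/dL: 0.85 × 70 × 70 / 57.6 = 72. Admitted.
- Man, 70 y, 95 kg, 1.0 mg/dL: 70 × 95 / 72 = 92. Not admitted.
- Woman, 65 y, 85 kg, 0.8 mg/dL: 0.85 × 75 × 85 / 57.6 = 94. Not admitted.

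For a 70-year-old of 70 kg, clearance equals 90 at a creatinine of 70 × 70 / (72 × 90) = 0.76 mg/dL in a man and 0.85 × 0.76 = 0.64 mg/dL in a woman. Anyone of that age and weight with a higher creatinine qualifies. The rule does exclude some patients, but it lets in others with ordinary creatinine.

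**Step 3. What zero cases would say about the CKD patients.** The CKD share is unknown, so it is varied as an assumption. Upper limit = 1 − 0.025^(1/m), where m is the number with CKD among the 40:

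| Assumed number with CKD | Exact 95% upper limit if none has ARN |
|---|---|
| 40 | 8.8% |
| 30 | 11.6% |
| 20 | 16.8% |
| 16 | 20.6% |
| 10 | 30.8% |

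The analysis plan quotes 17-37% for warfarin. With 20 CKD patients the limit lies just under the bottom of that range; with 16 it lies inside it.

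**The case against.** Much can fairly be said for the protocol. The rule admits every otherwise eligible CKD patient who is not on dialysis, and all participants are 60 or over, which section 3 also lists as a risk factor. Such a cohort is still plausibly at higher risk than people at large, so the closing inference is weakened rather than reversed. The 0-9% interval is tied explicitly to the planned sample size and is right for it. The limits of 16.8% and 20.6% belong to hypothetical subgroups and are not corrections to it. The unit is an evident slip beside the words creatinine clearance. All of this stands.

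Three stronger readings are tempting and are not supported:

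- *The cohort is not a high-risk group, because the rule hardly selects beyond age and atrial fibrillation.* The protocol gives no distribution of weight or creatinine, and the heavier patients in step 2 are excluded despite ordinary creatinine. Only the weaker statement holds: the cohort is not assured to be a CKD group.
- *The loss of incidence can be calculated by diluting the warfarin range.* The protocol gives 17-37% as the reported warfarin incidence, not as a figure for CKD patients alone. The title of one study cited for the range says that the condition occurs with and without CKD. The range may already be mixed, and neither the CKD share nor the relative risk is given.
- *The plan wrongly omits an analysis by kidney function.* The named predictors are given as examples, and further tables may sit in an analysis plan that is not shown.

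None of these points reconciles the CKD description with the entry criteria.

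**Conclusion.** The point holds as an internal mismatch with consequences for interpretation. Followed as written, the protocol would attach a CKD, highest-risk conclusion to patients whom its entry rule does not require to have CKD. The direction of any resulting bias favours the study's hypothesis; its size cannot be determined from the protocol.

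What can be sized is the loss of precision for the group named as the target. The zero-event upper limit is 8.8% if all 40 have CKD, and 16.8% or 20.6% if 20 or 16 do. This rests on the assumed CKD shares. The examples of who qualifies rest on Cockcroft-Gault with illustrative weights and creatinine values, and on the ordinary meaning of CKD, which the protocol does not define. Confidence is high for the mismatch and limited for how much it matters in practice.

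**What to change.** 1. Correct the unit of the clearance criterion to mL/min and name the formula.
2. In section 5(a) and the data analysis plan, describe the cohort as it is selected: age 60 or over with creatinine clearance at or below 90.
3. Report the primary incidence with exact 95% intervals by baseline creatinine clearance, using a split fixed in advance. Below 60 and 60-90 mL/min is one example; that cut-point is a convention and does not come from the protocol.
4. Rest any CKD, highest-risk or worst-case statement, including the reading of a negative result, on the lower-clearance stratum only.

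The cost is some rewording and one table. Age, sex, weight and baseline creatinine are already on the list of collected variables (Study Design, item e.vii), and recruitment is unaffected. The drawback is a wide interval in the lower stratum, as the table in step 3 shows for small numbers. That width reflects how much the study can actually say about those patients.

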The clinical trials that compared the NOACs to warfarin did not specifically study ARN and did not repeat creatinine and urinalysis testing in the first two to three months of therapy to establish possible ARN diagnosis [15-20]. In most of these studies, only baseline creatinine and creatinine levels 6 to 12 months later were analyzed, hence it is possible that ARN was under-diagnosed as most cases of ARN are detected in the first eight weeks of therapy. Our study aims to accurately capture ARN cases by making these measurements monthly in the first three months of starting the anticoagulant.

This study is pivotal because it will for the first time, define the incidence of ARN in patients on rivaroxaban or apixaban therapy. If we find that ARN incidence in patients started on rivaroxaban or apixaban is less than that seen with warfarin, this can help support evidence that this NOAC is safer for the kidneys compared to warfarin and this data can enable us make evidence based decisions regarding the continued use of the medication to help our patients. If on the other hand we find that the medication leads to ARN, then we will be contributing important post-marketing surveillance data that can also help us make safety decisions about the use of the medication in the future.

INNOVATION

Previous studies on ARN have utilized retrospective study designs which have many epidemiological pitfalls including the cause versus effect bias and the inability to ascertain relative risk [1]. Our study is unique because we intend to utilize a prospective epidemiological design to study this renal complication, a first in the study of ARN. This is important because ARN is a diagnosis of exclusion and hence a prospective study is able to more accurately define cases of the condition compared to the assumptions that are made in retrospective studies where further work up cannot be done in retrospect.

This will be the first epidemiological study focused on ARN in a NOAC. Even though NOACs are new, they are becoming ubiquitous and a mainstay in clinical practice and not just an alternative to warfarin. For example, the recent CHEST guidelines recommend them as first line therapy in the treatment of venous thromboembolism [8]. Hence it will be important to clearly delineate their effects on the kidneys.

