Secondary endpoint - Urinalysis measurements (particularly hematuria and proteinuria) will be analyzed for correlation with the incidence of ARN. Demographic variables including age and race will be analyzed in contingency tables using Fisher's exact test to ascertain if they are significant for the primary outcome.

- ii. Describe any primary or secondary safety endpoints (*e.g. any disease or symptom that would result in the withdrawal of that subject from the study*): Subjects will be censored from the study if anticoagulation is withdrawn for any clinical reason

e. Human Research Methods:

- i. Describe and explain the study design (*e.g. randomized, double-blind, placebo-controlled clinical trial or retrospective chart review*):

This is a prospective observational study designed to determine the incidence of ARN in 40 adult patients recently initiated on rivaroxaban or apixaban at Einstein Medical Center Philadelphia.

- ii. Describe all research activities involved in this protocol, including a study visit timeline if appropriate:

Baseline demographic data, past medical history, current medication list and baseline laboratory records (taken within the last three months) will be obtained from the patient's hospital chart and the electronic medical record. Serum creatinine and urinalysis measurements will then be repeated at monthly intervals for the first three months and then at the six-month mark. These laboratory tests will be drawn at Einstein's Klein building Suite 100 by a trained phlebotomist.

If AKI, defined as an increase in baseline serum creatinine ≥ 0.3 mg/dL from baseline, is noted in any study participant, the patient and his primary care physician or cardiologist will be notified both verbally and through a detailed letter. A standard clinical evaluation and work up will then be performed by the patient's primary care physician or cardiologist as part of the patient's usual care with referral to a nephrologist if necessary. The research team will then be notified of the result of this work up.

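### Entry up to four weeks after the first dose, with a baseline creatinine that need not pre-date it, can miss early ARN and tends to understate incidence by an unknown amount

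*Protocol*

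**What the plan says.** Under Study Design, b) Inclusion and Exclusion Criteria, a patient qualifies if "Participant has been initiated on long term anticoagulation with rivaroxaban or apixaban for atrial fibrillation within four weeks of recruitment". The exclusions there are blood dyscrasias or active bleeding, a history of hematuria, and dialysis.

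Section 3 (Background/Significance) says of ARN that "it usually occurs in the first two months of starting anticoagulant therapy", and its Significance part says that "most cases of ARN are detected in the first eight weeks of therapy". The same part criticises earlier trials for not measuring in this period and promises to do better by "making these measurements monthly in the first three months of starting the anticoagulant".

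Under Study Design, e) Human Research Methods, item ii, "baseline laboratory records (taken within the last three months) will be obtained from the patient's hospital chart and the electronic medical record". Then: "Serum creatinine and urinalysis measurements will then be repeated at monthly intervals for the first three months and then at the six-month mark". That sentence gives no time zero. Item iii of the same section refers to the six months after starting anticoagulation.

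The primary endpoint (d, Study Endpoints) is a creatinine rise of at least 0.3 mg/dL from baseline with no other obvious cause after work-up. On the analysis, both d) and g) Data Management say: "This incidence will be expressed as a percentage".

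**The concern.** Entry can come half-way through the period that the protocol itself regards as the time of highest risk. Whatever happens between the first dose and consent is observed only through the chart, and nothing in the protocol says how it is to be used. The baseline rule adds to this: for a late entrant, a chart value from the last three months may have been taken on the drug, after the creatinine had already risen.

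The direction of the error matters. The hypothesis (section 2) is that incidence is lower than reported for warfarin, and g) Data Management plans to read a negative result as very low risk in the general population. Missed early cases would support both statements. Because the protocol does not ask who was lost before consent, the extent of the problem could not be judged afterwards.

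**Working it through.** **1. The protocol's own figures.** Its only statistical figures are exact 95% intervals for 40 patients. Clopper-Pearson limits are 0 to 8.8% for 0 cases, 0.6% to 16.9% for 2 and 12.7% to 41.2% for 10. These agree with the stated 0–9%, 0.6–17% and 13–41%. The intervals are right, but they cover sampling error only and not cases missed before entry.

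**2. How an early case can be missed under the text.**
- The drug was stopped before recruitment. The criteria look for long-term anticoagulation and willingness to adhere, so such a patient is not a natural candidate.
- Bleeding, hematuria or dialysis arose after the first dose and is an exclusion by the time of screening. The protocol itself lists hematuria as a possible correlate of ARN.
- The rise resolved before the first study draw. If months are counted from enrolment, a week-4 entrant is first drawn at about week 8.
- The baseline was taken on the drug and was already raised, so no rise of 0.3 mg/dL shows.

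**3. How an early case is still counted.** No criterion excludes a creatinine rise since the first dose. If the patient stays on the drug, the baseline pre-dates it and the rise persists, the first study draw records it.

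**4. Size under stated assumptions.** Let
- p = true incidence. The protocol's sample-size text cites 17–37% for warfarin.
- s = share of cases that fall in weeks 0–8, spread evenly. The protocol says only that it is most of them.
- w = mean share of the eight weeks elapsed at entry: 2/8 = 0.25 if entry is uniform over weeks 0–4, and 4/8 = 0.5 if everyone enters at week 4.
- m = share of pre-entry cases that are lost.

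The protocol gives no value for s or m, and for entry only the four-week limit. The lost fraction of all patients is e = p × s × w × m, and the observed incidence is (p − e)/(1 − e).

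With s = 1 and p = 17%:

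| Entry | m | e | Observed | P(2 or fewer cases of 40) |
|---|---|---|---|---|
| any | 0 | 0 | 17.0% | 2.4% |
| uniform, weeks 0–4 | 0.5 | 0.02125 | 0.14875/0.97875 = 15.2% | 4.6% |
| uniform, weeks 0–4 | 1 | 0.0425 | 0.1275/0.9575 = 13.3% | 8.4% |
| all at week 4 | 1 | 0.085 | 0.085/0.915 = 9.3% | 26.9% |

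At p = 37% the four observed values are 37.0%, 33.9%, 30.6% and 22.7%. With s = 0.8 and m = 1, a true 17% appears as 14.1% (uniform entry) or 10.9% (all at week 4).

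**5. Direction.** The model above loses cases only. If a fraction a of cases and a fraction b of non-cases are lost, the observed incidence is p(1 − a)/[p(1 − a) + (1 − p)(1 − b)]. This is below p only when a exceeds b. As an assumed illustration, take p = 17%, a quarter of pre-entry cases lost under uniform entry (a = 0.25 × 0.25 = 0.0625) and b = 0.10. The result is 0.159375/(0.159375 + 0.747) = 17.6%, slightly above the truth.

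**The case against.** A reader might infer that early cases simply drop out before enrolment. The protocol does not support that. As step 3 shows, an early rise leaves the patient eligible, and it is counted when it persists against a pre-drug baseline. The larger figures in step 4 therefore rest on an assumed loss fraction of 100%, and the 9.3% also needs every patient to enter at the outer limit.

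Early entry is also provided for. A pharmacist checks new inpatient orders, the initiating cardiologist identifies clinic patients, and there is "a confidential report generated weekly by the Einstein's AECIS". Where testing is tied to drug start, even a day-0 entrant has no study draw before about week 4, so a rise that resolves sooner is missed whatever the entry date. Finally, the bias is not certain to be downward, because patients without ARN who bleed or stop the drug leave the denominator (step 5).

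All of this stands, and it limits the size and certainty of the claim. It does not remove the problem. Four weeks remains permitted, the baseline is not tied to the first dose, the schedule has no single time zero, and the baseline and exclusion routes remain open. Some reporting detail may sit in an analysis plan that is not shown, but the baseline definition and the time zero are fixed in this protocol.

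**Conclusion.** The point holds as a possible bias of unknown size. Late entry, combined with a baseline that may be taken on the drug, can miss some early ARN, and the simple percentage makes no allowance for it. A net understatement is the more plausible direction: each route in step 2 removes or hides cases, and the baseline and resolved-rise routes affect cases only. It is not established, because losses among non-cases work the other way.

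Under even spread of events and entry, a true 17% would be reported as something between 17% (no loss) and 13.3% (complete loss), with 9.3% as the extreme. These are scenarios and not estimates. The documents do not support saying that early cases are excluded as a rule, or that the bias can run in only one direction. The change is still worth making, because it is cheap and determines what a low observed incidence can be taken to mean.

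**What to change.** - Require the baseline creatinine to pre-date the first dose.
- Define time zero as the date of the first dose, and count follow-up and events from it throughout, including in e) Human Research Methods.
- In enrolled patients, count a chart-documented rise of at least 0.3 mg/dL between first dose and consent as AKI, subject to the same assessment for another cause as later rises.
- From the chart review already planned for every identified patient, report how many otherwise eligible patients had a creatinine rise or had stopped the drug before consent. Give the incidence with and without them.
- Use the existing new-order check and weekly report to approach patients early, and report the time from first dose to entry.

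The cost is protocol wording and slightly more screening work, with no extra blood draws and no change to treatment. A patient with no creatinine before the first dose could not be given a valid baseline, and the reported incidence may be less favourable if early cases are found.
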